[Part 2 of 2 of the document. The other parts are not shown.]

Licensed live attenuated vaccines should be given at least 28 days before or at least 28 days after a study vaccination. Other licensed (not live) vaccines (eg, influenza, tetanus, hepatitis A, hepatitis B, rabies) should be given more than 14 days before (or more than 14 days after, as per exclusion criterion 6) administration of study vaccine in order to avoid potential confusion of adverse reactions and potential immune interference. The use of any coronavirus vaccine (licensed or investigational) other than Ad26.COV2.S is disallowed at any time prior to vaccination and during the study except under the conditions described in Sections 6.3 and 6.8. If a vaccine is indicated in a post-exposure setting (eg, rabies or tetanus), it must take priority over the study vaccine. Receipt of another licensed/authorized COVID-19 vaccine by a study participant at any timepoint during the study must be recorded. The name and date(s) of administration of the COVID-19 vaccine should be recorded in the eCRF.

Chronic or recurrent use of systemic corticosteroidsa at immunosuppressive dose and administration of antineoplastic and immunomodulating agents or radiotherapy are prohibited during the study and within 6 months before the planned administration of the study vaccine. If any of these agents are indicated in a disease setting, these must take priority over the study vaccine.

Refer to Section 5.2 for further details of prohibited therapy.

The sponsor must be notified in advance (or as soon as possible thereafter) of any instances in which prohibited therapies are administered. The participant should remain in the study. Depending on the time of the occurrence, any participant who receives a prohibited concomitant therapy will not be included in the immunogenicity analyses.

## 6.11. Study Vaccination Pausing Rules for Stages 1a and 2a

A committee consisting of the representatives of the sponsor and collaboration partners, along with the principal investigator (the protocol safety review team [PSRT]) and the Janssen Medical Safety Council will monitor safety in a blinded manner, including the study vaccination pausing rules (applicable to Stages 1a and 2a only). Adverse events that may lead to the study vaccination pausing rules (applicable to Stages 1a and 2a only) are described below and will be assessed by the Janssen Medical Safety Council to confirm that the study pause is warranted.

The occurrence of any of the following events in Stages 1a and 2a will lead to a pause in further study vaccination:

---

a Note: Ocular, topical or inhaled steroids are allowed. █

1. Death of a participant, considered related to study vaccine or if the causal relationship to the study vaccine cannot be excluded; OR
2. One or more participants experience an SAE (solicited or unsolicited) that is determined to be related to study vaccine; OR
3. One or more participants experience anaphylaxis or generalized urticaria, clearly not attributable to other causes than vaccination with study vaccine.

To enable prompt response to a situation that could trigger pausing rules, the investigator should notify the sponsor's medical monitor or designee (AND fax or email the SAE form to Global Medical Safety Operations, if applicable), immediately and no later than 24 hours after becoming aware of any related SAE AND update the eCRF with relevant information on the same day the SAE information is collected (see also Section 8.3.1). Based on the pausing criteria, the sponsor's medical monitor or designee, in consultation with the Janssen Medical Safety Council, then decides whether a study pause is warranted and informs the DSMB of the decision. All sites will be notified immediately in the event of a study pause. The sponsor's medical monitor or designee is responsible for the immediate notification of DSMB members and coordination of a DSMB meeting in the event of a study pause.

The DSMB will review unblinded data and will make recommendations regarding the continuation of the study to the sponsor study team. Resumption of vaccinations will start only upon receipt of written recommendations by the DSMB. The clinical site(s) will be allowed to resume activities upon receipt of a written notification from the sponsor. The formal recommendation from the DSMB will be forwarded by the investigator to the IRB/IEC and by the sponsor to the relevant health authorities, according to local standards and regulations.

Vaccinations for an individual participant may be suspended for safety concerns other than those described in the pausing criteria, at the discretion of the investigator if he/she feels the participant's safety may be threatened. The sponsor's medical monitor or designee or the investigator(s) (upon consultation with the sponsor's medical monitor or designee) may initiate DSMB review for any single event or combination of multiple events which, in their professional opinion, could jeopardize the safety of the participants or the reliability of the data.

Vaccinations for the study may be suspended for safety concerns other than those described above, or before pausing rules are met, if, in the judgement of the DSMB, participant safety may be threatened.

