- A passive follow-up approach is adopted, defined as follow-up by the site at Month 18 and Month 24 to document new COVID-19 participant-reported episodes as SAEs, AEs, or MAAEs. Participants may contact the site at any time in between scheduled visits to report COVID-19 episodes.
- Concomitant medications for these events should be reported.
- If a COVID-19 confirmatory laboratory or assay read-out is available, this should be reported in the eCRF (self-reported or as part of CIOMS form).
- Participants may contact the site at any time in between scheduled visits to report COVID-19 episodes.
- Events ongoing at time of informed consent do not need to be reported as AEs, SAE, or MAAEs, only new onset of COVID-19 events need to be reported.
- 90% of the participants who received a booster vaccination will be monitored for safety until 1 year post booster vaccination. The remaining 10% of the active participants who receive a booster vaccination will be monitored for safety at least for 6 months.

For participants in the Safety Subset (double-blind phase):

- Solicited AEs, collected through an e-Diary, will be recorded from the time of vaccination until 7 days post-vaccination.
- All other unsolicited AEs, whether serious or non-serious, will be recorded from the time of vaccination until 28 days post-vaccination.

Up to Amendment 7: For all participants who received booster vaccination at the Year 1/Booster Visit:

- Solicited AEs, collected through an e-Diary, will be recorded from the time of vaccination until 7 days post-vaccination. All participants will collect signs and symptoms in the e-Diary, if feasible. For a subset of participants, ie, participants included in the Safety Subset of the double-blind study phase and all participants who received a heterologous COVID-19 vaccination outside the study, the e-Diary will be reviewed by the study personnel and solicited AEs recorded in the eCRF, if feasible. All other unsolicited AEs, whether serious or non-serious, will be recorded from the time of vaccination until 28 days post-vaccination for all participants who received the booster at Year 1/Booster Visit.

As of Amendment 7, solicited and unsolicited AE reporting will stop for all participants.

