##### **Not Related**

There is not a reasonable causal relationship between study vaccine administration and the AE.

The term “reasonable causal relationship” means there is evidence to support a causal relationship.

By definition, all solicited AEs at the injection site (local) will be considered related to the study vaccine administration.

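### Section 6.11 makes anaphylaxis or generalized urticaria a pausing trigger whatever its seriousness, but its 24-hour notification duty covers related SAEs only

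*Protocol*

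**What the plan says.** Protocol Section 6.11 names three events, any one of which leads to a pause in vaccination in Stages 1a and 2a:

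1. "Death of a participant, considered related to study vaccine or if the causal relationship to the study vaccine cannot be excluded"
2. "One or more participants experience an SAE (solicited or unsolicited) that is determined to be related to study vaccine"
3. "One or more participants experience anaphylaxis or generalized urticaria, clearly not attributable to other causes than vaccination with study vaccine"

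The next paragraph opens with its purpose: "To enable prompt response to a situation that could trigger pausing rules". It then tells the investigator to notify the sponsor's medical monitor "immediately and no later than 24 hours after becoming aware of any related SAE AND update the eCRF" on the same day, and refers the reader to Section 8.3.1. After that notification the medical monitor, with the Medical Safety Council, decides whether a pause is warranted and informs the DSMB.

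Section 10.3.6 (Independent Data Monitoring Committee) ties the DSMB's ad hoc review under Section 6.11 to SAEs that lead to a pausing situation.

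**The concern.** The trigger list and the sentence that serves it differ in scope. Triggers 1 and 2 concern deaths and SAEs. Trigger 3 is defined by the type of event and by its cause, and says nothing on seriousness. The notification duty is limited by seriousness. A site that follows the text literally may see an event that the protocol says pauses vaccination, yet have no instruction to tell the medical monitor within 24 hours.

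A pausing rule stops further exposure only if the event reaches the decision-makers promptly. Stages 1a and 2a each enrol 2,000 participants (Section 9.9), and a late report means that further participants in that age group are vaccinated although a listed criterion has been met.

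**Working it through.** No arithmetic decides this point. The check sets each trigger beside every 24-hour duty in the part of the protocol reviewed.

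**Step 1: what trigger 3 adds to the list.** Trigger 3 already requires that vaccination be the clear cause, so an event that meets it is related by construction. If it is also serious, trigger 2 catches it. Trigger 3 therefore extends the list only through non-serious events.

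**Step 2: the Section 6.11 sentence.** It covers related SAEs, and its same-day eCRF update is tied to SAE information. The part of trigger 3 that trigger 2 does not already cover falls outside it.

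**Step 3: other reporting routes.**

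- Section 8.3.1 and Appendix 4 (Section 10.4.5), SAEs: 24 hours to the sponsor, whatever the causality, but SAEs only.
- Section 8.3.7 and Section 10.4.5, AESIs: 24 hours irrespective of seriousness, but AESIs here are thrombotic events and thrombocytopenia, assessed as suspected TTS. Urticaria and anaphylaxis are not among them.
- Section 8.3.1, medically-attended AEs: collected for 6 months after each vaccination, with no 24-hour limit.
- Section 8.3.1, Safety Subset: "All other unsolicited AEs, whether serious or non-serious, will be recorded from the time of vaccination until 28 days post-vaccination", again with no 24-hour limit.
- The remaining 24-hour duties concern pregnancies (Section 8.3.5) and product quality complaints (Section 10.4.6).

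**Step 4: slower backstops.**

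- At least 30 minutes of on-site observation for the first 2,000 participants in each age group (Section 8.3.2). This can detect an early reaction, but sets no deadline for passing it on and cannot detect a later one.
- DSMB review of Day 1 to Day 3 data (Sections 9.9 and 10.3.6). It is not limited to serious events, but it comes at the end of Stage 1a or 2a.
- Discretionary DSMB review at the request of the investigator or medical monitor (Section 6.11), the DSMB being told of adverse events of concern, and the safety data review by the PSRT and Medical Safety Council (Section 10.3.6). None has a stated deadline.

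**Step 5: coverage by trigger.**

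| Event | 6.11 sentence | Other 24-hour duty |
|---|---|---|
| Related death | yes | yes, as an SAE |
| Death with causality not excluded but not rated related | no, read literally | yes, as an SAE |
| Related SAE | yes | yes |
| Serious anaphylaxis or urticaria meeting trigger 3 | yes | yes |
| Non-serious generalized urticaria, or anaphylaxis judged non-serious, meeting trigger 3 | no | none found |

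Only the last row has no 24-hour route.

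**The case against.** The case on the other side has several parts.

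**Deaths.** A reader might infer that some deaths escape too. Trigger 1 includes a death "if the causal relationship to the study vaccine cannot be excluded", whereas Section 10.4.2 offers only Related or Not Related, and a reasonable causal relationship "means there is evidence to support a causal relationship". The protocol does not support that inference. Under Section 10.4.5 a death is an SAE whether or not it is linked to the vaccine, and Section 8.3.1, to which Section 6.11 refers, requires all SAEs within 24 hours. The medical monitor and the Medical Safety Council can then apply trigger 1 to any reported death. Only a difference in wording remains, and no listed death goes without a 24-hour report.

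**Anaphylaxis.** It will usually meet the life-threatening or medically important criterion in Section 10.4.1 and so be a related SAE. This stands, and it narrows the gap mainly to non-serious generalized urticaria.

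**Collection.** A reader might also infer that non-serious events outside the Safety Subset are never recorded unless medically attended. That is not shown to apply here. The Safety Subset has about 6,000 participants (Section 9.2.4.1) and Stages 1a and 2a together have 4,000. Their overlap is not stated in the part of the protocol reviewed. Membership would settle collection, but not the missing 24-hour route.

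**Backstops.** They exist, so it would be too strong to say that such an event would be missed. The supported statement is that it has no stated 24-hour route to the pause decision.

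**Timing.** No further participants are to be recruited (Sections 9.2.1 and 9.8), so a change now is unlikely to alter a Stage 1a or 2a decision. This is fair. Section 6.11 nevertheless remains current text, and the visit-window paragraph in Section 8 still refers to it for pauses affecting the Month 6/Unblinding Visit.

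**Conclusion.** The concern holds for trigger 3. Section 6.11 lists the event as leading to a pause whatever its seriousness, then limits the notification meant to serve the list to related SAEs. Section 10.3.6 repeats the SAE-only wording. A non-serious generalized urticaria, or an anaphylaxis judged non-serious, thus has no stated 24-hour route to the people who decide on the pause.

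The size is the non-serious part of one trigger out of three, in two stages of 2,000 participants each. It should not be expressed as a probability. With 1:1 randomization about 1,000 participants per stage receive vaccine, and assumed rates of 0.05%, 0.1% and 0.3% would give at least one event with probability 1 − (1 − r)^1000 = 39%, 63% and 95%. The protocol gives no such rate, and the formula describes the occurrence of an event, not a delayed notification or a missed pause. The contradiction does not depend on these figures.

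The conclusion assumes that no wider notification duty stands in the first part of the protocol, which was not available for this review.

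**What to change.** Reconcile the scope of the notification sentence in Section 6.11 with the three triggers listed above it, so that each listed trigger has a stated notification route and deadline. Make the matching change to the SAE-only wording on ad hoc DSMB review in Section 10.3.6. The pausing criteria themselves are not in question, and no new item on the SAE form is needed.

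The cost is two rewordings and, in use, a few more urgent notifications for reactions that turn out not to be serious.

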## **7. DISCONTINUATION OF STUDY VACCINATION AND PARTICIPANT DISCONTINUATION/WITHDRAWAL**

### **7.1. Discontinuation of Study Vaccination**

Not applicable.

## 7.2. Participant Discontinuation/Withdrawal From the Study

A participant will be withdrawn from the study for any of the following reasons:

- Lost to follow-up
- Withdrawal of consent
- Death
- Repeated failure to comply with protocol requirements

When a participant withdraws before study completion, the reason for withdrawal is to be documented in the eCRF and in the source document. If the reason for withdrawal from the study is withdrawal of consent then no additional assessments are allowed.

### Withdrawal of Consent

A participant declining to return for scheduled visits does not necessarily constitute withdrawal of consent. Alternate follow-up mechanisms that the participant agreed to when signing the consent form apply as local regulations permit.

#### 7.2.1. Withdrawal From the Use of Research Samples

##### Withdrawal From the Use of Samples in Future Research

The participant may withdraw consent for use of samples for research (refer to Long-Term Retention of Samples for Additional Future Research in Section 10.3.5 in [Appendix 3](#)). In such a case, samples will be destroyed after they are no longer needed for the clinical study. Details of the sample retention for research are presented in the main ICF.

### 7.3. Lost to Follow-up

To reduce the chances of a participant being deemed lost to follow-up, prior to randomization attempts should be made to obtain contact information from each participant, eg, home, work, and mobile telephone numbers and email addresses for both the participant as well as appropriate family members.

A participant will be considered lost to follow-up if he or she repeatedly fails to return for scheduled visits and is unable to be contacted by the study site. A participant cannot be deemed lost to follow-up until all reasonable efforts made by the study-site personnel to contact the participant are deemed futile. The following actions must be taken if a participant fails to return to the study site for a required study visit:

- The study-site personnel must attempt to contact the participant to reschedule the missed visit as soon as possible, to counsel the participant on the importance of maintaining the assigned visit schedule, to ascertain whether the participant wishes to or should continue in the study.
- Before a participant is deemed lost to follow-up, the investigator or designee must make every reasonable effort to regain contact with the participant (where possible, 3 telephone calls, e-mails, fax, and, if necessary, a certified letter to the participant's last known mailing address,

or local equivalent methods). Locator agencies may also be used as local regulations permit. These contact attempts should be documented in the participant's medical records.

- Should the participant continue to be unreachable, they will be considered to have withdrawn from the study.

Should a study site close, eg, for operational, financial, or other reasons, and the investigator cannot reach the participant to inform them, their contact information will be transferred to another study site.

## 8. STUDY ASSESSMENTS AND PROCEDURES

### Overview

The [Schedules of Activities](#) summarize the frequency and timing of all measurements applicable to this study.

Up to Amendment 7, all participants will be provided access to an eCOA digital tool. This eCOA will be used to collect COVID-19 signs and symptoms surveillance info for all participants, ePRO (Symptoms of infection with Coronavirus-19 [SIC], including body temperature, and pulse oximetry results) for all participants at baseline and in case of COVID-19-like signs and symptoms, and e-Diary data on 7-day reactogenicity (solicited signs and symptoms, including body temperature) in the Safety Subset and all participants who receive booster vaccination at the Year 1/Booster Visit, if feasible. All eCOA assessments should be conducted/completed before any tests, procedures, or other consultations to prevent influencing participant responses. Refer to the PRO completion guidelines for instructions on the administration of ePROs.

As of Amendment 7, the number of on-site visits for participants who are not part of the Immunogenicity or Booster Subsets is reduced. For these participants, any outstanding Visits 8 and 9 are cancelled. In addition, any outstanding Visits 10 and 11 are replaced by a phone call. No further booster vaccination will be provided in the protocol. In addition, requirements for COVID-19 episodes reporting are changed (ie, a passive follow-up approach is adopted, defined as safety follow-up by the site at Month 18 and Month 24 to document COVID-19 participant-reported events as SAE, AE, or MAAE until end of study). All participants will be reconsented at an unscheduled visit and as per local informed consent process guidelines.

If multiple assessments are scheduled for the same timepoint, it is recommended that procedures be performed in the following sequence: vital signs before blood draws. If needed, assessments may be performed on another day within the applicable visit window. Actual dates and times of assessments will be recorded in the source document, the eCRF, or the sample requisition form.

Up to Amendment 7, all participants will be provided a thermometer to measure body temperature if they experience COVID-19-like signs and symptoms. Participants in the Safety Subset and all participants who receive booster vaccination at the Year 1/Booster Visit will be provided a ruler (to measure local injection site reactions) and a participant e-Diary in the eCOA digital tool to record body temperature and solicited local (at injection site) and systemic signs and symptoms. The e-Diary includes instructions on how to capture the data and grading scales to assess severity

of the signs and symptoms post-vaccination (reactogenicity). The study staff is responsible for providing appropriate training to the participant to avoid missing or incorrect data. The e-Diary from participants in the Safety Subset (double-blind phase) and a subset of participants who received booster vaccination at the Year 1/Booster Visit, ie, participants included in the Safety Subset of the double-blind phase and all participants who received a heterologous prime or heterologous additional COVID-19 vaccination outside the study, if feasible, will be reviewed by the study personnel at visits indicated in the [Schedules of Activities](#). If the e-Diary review is missed, the diary will be reviewed during the following visit. All participants will also be provided with a kit to collect nasal swabs samples and recipients to collect saliva (see Section [8.1.2](#)).

The total blood volume to be collected over the course of the study from each participant will be approximately a maximum of 168.5 mL for participants in the immunogenicity subsets and a maximum of 72.0 mL for the other participants. Additional blood samples (up to 35 mL) will be collected from participants that experience COVID-19-like signs and symptoms meeting prespecified criteria for suspected COVID-19. For participants who experience a suspected AESI, an additional 30 mL of blood will be collected. Refer to the [Schedules of Activities](#) for the total blood volume (serum and, as applicable, whole blood samples) to be collected at each visit, over the complete course of the study, and in the event of a suspected COVID-19 episode. Repeat or unscheduled samples may be taken for safety reasons or for technical issues with the samples.

If allowed by local regulation, study visits may take place at the participant's home or other location in the event of ongoing SARS-CoV-2 transmission in the area of the participant. If possible and allowed per local regulation, visits, except screening and vaccination visits, can be performed by a phone call or a telemedicine contact, provided that assessments requiring a face-to-face interaction between the participant and a trained health care professional (including but not limited to blood sampling) are performed by a site staff member or a designee at the participant's home or other location, whichever is applicable. Conversely, in case of home visit, assessments that cannot be delegated to a designee must be performed by an appropriate site staff member via a phone call or telemedicine.

